3.10.3 Concomitant Medication for Subjects with MM

For subjects with MM, the first 6 subjects enrolled will receive acalabrutinib 100 mg BID and ACP-319 at the dose level determined from the escalation portion of the study. The last 6 subjects enrolled will receive acalabrutinib 100 mg and ACP-319 at the same level as the first 6 subjects and will concomitantly receive 40 mg dexamethasone once weekly. This study will use commercially available dexamethasone. Refer to the appropriate dexamethasone package insert for storage and handling instructions and warnings and precautions.

3.10.4 Required Concomitant Medications

Serious and fatal infections have occurred with idelalisib (a drug similar to ACP-319) including opportunistic infections such as *Pneumocystis jirovecii* pneumonia (PJP) and CMV (ZYDELIG [Summary of Product Characteristics]). Therefore, due to possible risk of class effects, prophylaxis for PJP in accordance with local guidelines and institutional standards should be administered to all subjects throughout ACP-319 treatment, and for a period of 2 to 6 months after the last dose of ACP-319. The duration of post-treatment prophylaxis should be based on clinical judgment and may take into account a subject's risk factors such as concomitant corticosteroid treatment and prolonged neutropenia. CMV testing will be required for subjects receiving ACP-319 treatment (see Section 4.1.24).

3.11 RISKS ASSOCIATED WITH STUDY DRUGS

3.11.1 Risks Associated with Acalabrutinib Treatment

The following summarizes the experience with acalabrutinib in hematological cancer studies. Full details regarding the clinical safety of acalabrutinib are presented in Sections 5 and 6 of the acalabrutinib Investigator Brochure.

Hemorrhage

Serious hemorrhagic events, including fatal events, have occurred in clinical trials with acalabrutinib.

The mechanism for hemorrhage is not well understood. Patients receiving antithrombotic agents may be at increased risk of hemorrhage. Use caution with antithrombotic agents and consider additional monitoring for signs of bleeding when concomitant use is medically necessary. Consider the benefit-risk of withholding acalabrutinib for at least 3 days pre- and post-surgery. Subjects with hemorrhage

Protocol: ACE-LY-001

should be managed per institutional guidelines with supportive care and diagnostic evaluations as clinically indicated.

Infections

Serious infections (bacterial, viral, and fungal), including fatal events, have occurred in clinical studies with acalabrutinib. The most frequent reported Grade ≥3 infection was pneumonia (preferred term). Across the acalabrutinib clinical development program (including subjects treated with acalabrutinib in combination with other drugs), cases of hepatitis B virus (HBV) reactivation, aspergillosis, and progressive multifocal leukoencephalopathy (PML) have occurred.

Consider prophylaxis in subjects who are at increased risk for opportunistic infections. Subjects should be monitored for signs and symptoms of infection and treated as medically appropriate. Refer to Section 3.11.6, Section 4.1.13, and Appendix 6 for additional information and monitoring guidance for viral hepatitis and Section 3.11.7 for additional information and management guidance for signs and symptoms of PML.

Cytopenias

Treatment-emergent Grade 3 or 4 events of cytopenias, including neutropenia, anemia, and thrombocytopenia have occurred in clinical studies with acalabrutinib. Monitor blood counts as specified in the schedule of assessments (Appendix 5) and as medically appropriate. Please refer to Section 3.8 for study drug modification guidance. Subjects with cytopenias should be managed according to institutional guidelines with maximal supportive care and diagnostic evaluations as clinically indicated. Subjects should be closely monitored as appropriate.

Second Primary Malignancies

Second primary malignancies, including solid tumors and skin cancers, have been reported in patients treated with acalabrutinib. The most frequent second primary malignancy was skin cancer (basal cell carcinoma). Subjects should be monitored for signs and symptoms of malignancy. Subjects who develop a second primary malignancy should be managed according to institutional guidelines with diagnostic evaluations as clinically indicated, and it may be necessary for subjects to permanently discontinue study treatment. Continuation of acalabrutinib treatment should be discussed with the medical monitor. Please refer to Section 6.3.3 for reporting guidance.

Protocol: ACE-LY-001

Atrial Fibrillation

Events of atrial fibrillation/flutter have occurred in clinical studies with acalabrutinib, particularly in subjects with cardiac risk factors, hypertension, diabetes mellitus, acute infections, or a previous history of atrial fibrillation.

Monitor for symptoms of atrial fibrillation and atrial flutter (e.g., palpitations, dizziness, syncope, chest pain, dyspnea) and obtain an ECG as appropriate. Subjects with atrial fibrillation should be managed per institutional guidelines with supportive care and diagnostic evaluations as clinically indicated.

3.11.2 Dietary Restrictions

Because acalabrutinib is metabolized by CYP3A (refer to the acalabrutinib Investigator Brochure for details), subjects should be strongly cautioned against the use of herbal remedies or dietary supplements (in particular, St John's wort, which is a potent CYP3A inducer).

Subjects should be encouraged to follow instructions related to eating relative to study drug administration (Section 3.4.3).

3.11.3 Drug-Drug Interactions

The concomitant use of strong inhibitors/inducers of CYP3A with acalabrutinib should be avoided when possible (see Appendix 3). If a subject requires short-term treatment with a strong CYP3A inhibitor (such as anti-infectives for up to 7 days), interrupt acalabrutinib treatment. Refer to Table 3-3 for dose modifications due to required short-term use of moderate or strong CYP3A inhibitors.

Avoid coadministration of strong CYP3A inducers. If a subject requires treatment with a strong CYP3A inducer, increase the acalabrutinib dose to 200 mg BID during concomitant administration with the strong inducer and return to recommended dose of 100 mg BID after stopping the strong CYP3A inducer.

Use of proton-pump inhibitors, H2 receptor antagonists, or antacids while taking acalabrutinib has the potential to decrease acalabrutinib exposure. If treatment with a gastric acid reducing agent is required, consider using an H2-receptor antagonist (2 hours after acalabrutinib) or antacid (2 hours before or 2 hours after acalabrutinib). Avoid coadministration with proton-pump inhibitors.

Protocol: ACE-LY-001

Table 3-3. Instructions for Coadministration of Drugs with Acalabrutinib

| Coadministered Drug | Acalabrutinib |
|-----------------------------------------|---------------------------------------------------------------------------------------------------------|
| Strong CVD2A inhibitor | Avoid concomitant use with acalabrutinib. If the inhibitor |
| Strong CYP3A inhibitor | will be used short-term (such as anti-infectives for up to 7 days), interrupt acalabrutinib. |
| Moderate CYP3A inhibitor | Decrease acalabrutinib dose to 100 mg QD |
| Strong CYP3A inducer | Avoid concomitant use. If concomitant use cannot be avoided, increase acalabrutinib dose to 200 mg BID. |
| Moderate CYP3A inducer | No change |
| P-gp inhibitor | No change |
| BCRP inhibitor | No change |
| Narrow therapeutic index P-gp substrate | No change |
| Bile acid sequestrants | No change |
| Statin (OATP substrate) | No change |
| Proton pump inhibitors | Avoid concomitant use. |
| H2-receptor antagonists | Take acalabrutinib 2 hours before taking a H2-receptor antagonist. |
| Antacids | Separate dosing by at least 2 hours. |

BCRP = breast cancer resistance protein; BID = twice daily; CYP = cytochrome P450; H = histamine; OATP = organic-anion-transporting polypeptide; P-gp = P-glycoprotein; QD = once daily.

3.11.4 Reproductive Toxicity

Women of Childbearing Potential

WOCBP are women who are fertile following menarche and until becoming postmenopausal unless permanently sterile; permanent sterilization methods include hysterectomy, bilateral salpingectomy, and bilateral oophorectomy.

Subjects of Non-Reproductive Potential

Women are considered to be of non-reproductive potential if they meet any of the below criteria:

Postmenopausal, defined as at least 12 months with no menses without an alternative medical cause; in women <45 years of age a high follicle-stimulating hormone (FSH) level in the postmenopausal range may be used to confirm a postmenopausal state in women not using hormonal contraception or hormonal replacement therapy. In the absence of 12 months of amenorrhea, a single FSH measurement is insufficient.

Have had a hysterectomy and/or bilateral oophorectomy, bilateral salpingectomy, or bilateral tubal ligation/occlusion, at least 6 weeks before Screening

Have a congenital or acquired condition that prevents childbearing

Men are considered to be of non-reproductive potential if they are permanently sterile due to bilateral orchidectomy.

Protocol: ACE-LY-001

Highly Effective Methods of Contraception

Highly effective methods of contraception (to be used during heterosexual activity) are defined as methods that can achieve a failure rate of <1% per year when used consistently and correctly. Such methods include:

Combined (estrogen and progestogen containing) hormonal contraception associated with inhibition of ovulation, which may be oral, intravaginal, or transdermal

Progestogen-only hormonal contraception associated with inhibition of ovulation, which may be oral, injectable, or implantable

Intrauterine device or intrauterine hormone-releasing system

Bilateral tubal occlusion

Vasectomy of a female subject's male partner (with medical assessment and confirmation of vasectomy surgical success)

Sexual abstinence (only if refraining from heterosexual intercourse during the entire period of risk associated with the study treatments)

Hormonal contraception may be susceptible to interaction with study or other drugs, which may reduce the efficacy of the contraception method.

Abstinence (relative to heterosexual activity) can only be used as the sole method of contraception if it is consistently employed during the entire period of risk associated with the study treatments as the subject's preferred and usual lifestyle.

Periodic abstinence (e.g., calendar, ovulation, sympto-thermal, and post-ovulation methods) and withdrawal (coitus interruptus), spermicides only, and lactational amenorrhea method are not acceptable methods of contraception. Female condom and male condom should not be used together as an effective method of contraception.

If a contraceptive method is restricted by local regulations/guidelines, then it does not qualify as an acceptable method of contraception for subjects participating at sites in the relevant country/region.

3.11.5 Overdose Instructions

For any subject experiencing an acalabrutinib overdose (ingestion of more than the recommended dosage), observation for any symptomatic side effects should be instituted, and vital signs, biochemical and hematologic parameters, and ECGs should be followed closely (consistent with the protocol or more frequently, as needed). Appropriate supportive management to mitigate adverse effects should be initiated. If the overdose ingestion is recent and substantial, and if there are no medical contraindications, use of gastric lavage or induction of emesis may be considered.

Protocol: ACE-LY-001

The medical monitor must be contacted if a study drug overdose occurs.

3.11.6 Hepatitis B Virus Reactivation

Serious or life-threatening reactivation of viral hepatitis may occur in subjects treated with acalabrutinib, obinutuzumab, or rituximab. Increased risk of infections including viral hepatitis may also occur in subjects treated with standard chemotherapy including cyclophosphamide and bendamustine. Refer to Section 4.1.13 for details on viral hepatitis screening and monitoring for this study.

3.11.7 Progressive Multifocal Leukoencephalopathy

Serious or life-threatening occurrence of PML may occur in subjects treated with acalabrutinib, obinutuzumab, or rituximab. Increased risk of infections including PML may also occur in subjects treated with standard chemotherapy including fludarabine and cyclophosphamide.

Signs and symptoms of PML may include cognitive and behavioral changes, language disturbances, visual disturbances, sensory deficits, weakness, and coordination and gait difficulties.

If PML is suspected, hold further study treatment (as applicable, based on risks in the acalabrutinib Investigator Brochure or local prescribing information) until PML is excluded. A diagnostic evaluation may include (but is not limited to):

Neurologic consultation

Brain magnetic resonance imaging

PCR analysis for John Cunningham or JC virus DNA in cerebrospinal fluid

If PML is confirmed, permanently discontinue study treatment (as applicable, based on risks in the acalabrutinib Investigator Brochure or local prescribing information).

3.12 WITHDRAWAL OF SUBJECTS FROM STUDY TREATMENT

All study participants may receive acalabrutinib as long as they are safely benefitting; however:

The investigator, in consultation with the medical monitor, may withdraw any subject from study treatment, if, in the investigator's opinion, it is not in the subject's best interest to continue.

Any subject has the right to withdraw from the study at any time.

Protocol: ACE-LY-001

Any subject whose study treatment is delayed (i.e., has not received acalabrutinib) for >28 consecutive days due to study drug-related toxicity should be withdrawn from study treatment, unless reviewed and approved by the medical monitor.

Any subject who has confirmed objective evidence of cancer progression while receiving study treatment at the highest individual tolerable dose level allowed in the protocol (see Section 3.5 and Section 3.8) should be withdrawn from the study treatment. Note: If there is uncertainty regarding whether there is cancer progression, the subject may continue study treatment and remain under close observation (e.g., evaluated at 4- to 8-week intervals) pending confirmation of progression. Transient worsening of disease during temporary interruption of study therapy (e.g., for drug-related toxicity, surgery, or intercurrent illness) may not indicate disease progression. In such circumstances, and if medically appropriate, subjects may resume therapy and relevant clinical, laboratory, and/or radiographic assessments should be done to document whether tumor control can be maintained or whether actual disease progression has occurred.

Any subject who is unable to tolerate a rechallenge at the lowest recommended dose of acalabrutinib (see Section 3.8) should be discontinued from the study treatment unless continued therapy is permitted by the medical monitor. Note: If medically appropriate, subjects may continue with protocol-specified therapy for acalabrutinib if the therapeutic agent continues to be tolerated.

Any subject whose medical condition substantially changes after entering the study should be carefully evaluated by the investigator in consultation with the medical monitor. Such subjects should be withdrawn from study treatment if continuing would place them at risk.

Any subject who becomes pregnant should be removed from study treatment.

Any subject who becomes significantly noncompliant with study drug administration, study procedures, or study requirements should be withdrawn from study treatment in circumstances that increase risk or substantially compromise the interpretation of study results.

Subjects who discontinue study therapy will continue on study for safety (Section 4.3), disease progression, and time-to-next therapy (Section 4.4) for their lymphoid cancer unless they withdraw consent for further follow-up. Thus, all subjects receiving ≥1 dose of study drug will be followed during the immediate post-therapy period unless the subject withdraws consent for such follow-up to be conducted. The date the subject is

Protocol: ACE-LY-001

withdrawn from study treatment or from the study (including post-therapy follow-up) and the reason for discontinuation will be recorded and also should be described on the appropriate CRF.

3.13 REASONS FOR STUDY EXIT

Reasons for study exit include:

Subject's withdrawal of consent from study

Decision by sponsor to terminate the study

Disease progression

Start of alternative anticancer therapy

Subject lost to follow-up

Death

3.14 DATA AND SAFETY MONITORING

This study will be monitored in accordance with the sponsor's pharmacovigilance procedures. AEs and SAEs will be reviewed as part of ongoing safety surveillance. The sponsor will contact the investigators and applicable site staff regularly to discuss study progress, obtain investigator feedback and exchange, and discuss "significant safety events" (i.e., AEs leading to dose reductions, related SAEs, and deaths). In addition, in Part 1, mandatory safety teleconferences will occur before enrollment of subjects into the next cohort. In Part 2, teleconferences with investigators and applicable site staff will be conducted, or written communications sent, to discuss study progress, obtain investigator feedback and exchange, and discuss "significant safety events" (i.e., AEs leading to dose reductions, related SAEs, and deaths) on an as needed basis.

4.0 STUDY ACTIVITIES AND ASSESSMENTS

The schedule of events is provided in Appendix 5. Descriptions of the scheduled evaluations are outlined below and complete information on study drug and dosing is provided in Section 3.5.

Before study entry, throughout the study, and at the follow-up evaluation, various clinical and diagnostic laboratory evaluations are required. The purpose of obtaining these detailed measurements is to ensure adequate safety and tolerability assessments. Clinical evaluations and laboratory studies may be repeated more frequently if clinically indicated.

Protocol: ACE-LY-001

4.1 DESCRIPTION OF PROCEDURES

4.1.1 Informed Consent

The subject must read, understand, and sign the institutional review board (IRB)/independent ethics committee (IEC)-approved ICF confirming his or her willingness to participate in this study before initiating any screening activity that is not considered standard of care by institutional standards. Subjects must also grant permission to use protected health information if required by local regulations.

4.1.2 Medical History

Collect and record the subject's complete history through review of medical records and by interview. Concurrent medical signs and symptoms must be documented to establish baseline severities. A disease history, including the date of initial diagnosis and list of all prior anticancer treatments, and responses and duration of response to these treatments, also will be recorded.

4.1.3 Adverse Events

The accepted regulatory definition for an AE is provided in Section 6.2. All medical occurrences from the time of first dose that meet this definition must be recorded. Important additional requirements for reporting SAEs are explained in Section 6.3.

4.1.4 Concomitant Medications and Therapy

Document all concomitant medications and procedures from within 21 days before the start of study drug administration through 30 days after the last dose of study drug.

4.1.5 Confirmation of Eligibility

Subject eligibility for enrollment will be assessed per Section 3.3. All screening procedures, unless otherwise indicated, should be completed within 21 days of the first dose of study drug.

Appendix 1.

Protocol: ACE-LY-001

4.1.7 Physical Examination, Vital Signs, Height, & Weight

The screening physical examination will include, at a minimum, the general appearance of the subject, height (screening only) and weight, and examination of the skin, eyes, ears, nose, throat, lungs, heart, abdomen, extremities, musculoskeletal system, nervous system, and lymphatic system.

Symptom-directed physical examinations will be done during the treatment period and at the SFU visits.

For all subjects except those with MM, the following B symptoms will be collected at each examination:

Unintentional weight loss of normal body weight over a period of ≤6 months

Disease associated intermittent fevers ≥38 °C

Drenching sweats especially at night

Vital signs (blood pressure, heart rate, and body temperature) will be assessed after the subject has rested in the sitting position.

4.1.8 Bone Marrow Aspirate and Biopsy

A bone marrow aspirate and biopsy will be done at screening or up to 60 days before the first dose of study drug. Per the current response criteria (Bladé et al. 1998; Durie et al. 2006; Hallek et al. 2008; Owen et al. 2013; and Cheson et al. 2014), a bone marrow aspirate/biopsy will also be required at any time on study to confirm a complete response (CR). A bone marrow aspirate and biopsy will also be done at end of Cycle 12, and as clinically indicated. For subjects continuing study treatment beyond Cycle 12, bone marrow aspirate and biopsy to be done at investigator discretion, per standard of care. Testing will be performed at the study center's local laboratory or other clinical laboratory listed on the investigator's Form Food and Drug Administration (FDA) 1572. De-identified copies of all bone marrow biopsy/aspirate results may be requested by the sponsor.

When available, any unused bone marrow tissue will be used for exploratory correlative studies (Section 4.1.20). Correlative studies on bone marrow tissue will be done by the sponsor. Refer to the laboratory manual for sample handling and shipment instructions.

Protocol: ACE-LY-001

4.1.9 Electrocardiogram

A centralized cardiac safety monitoring laboratory will be used in this study to assess the potential of acalabrutinib and ACP-319 as evaluated by ECG measurement of the QTc interval.

Toxicity grading of QTc interval prolongation will be defined by CTCAE and provided in Table 4-1.

Table 4-1. QTc Toxicity Grading Defined by CTCAE

| Grade | Definition |
|-------|--------------------------------------------------------------------------------------------------------------------------------------------------|
| 1 | QTc 450 to 480 ms |
| 2 | QTc 481 to 500 ms |
| 3 | QTc ≥501 ms on at least 2 separate ECGs |
| 4 | QTc ≥501 ms or >60 ms change from baseline or Torsades de pointes or polymorphic ventricular tachycardia or signs/symptoms of serious arrhythmia |

Abbreviations: CTCAE = Common Terminology Criteria for Adverse Events; ECG = electrocardiogram.

The service provider will provide the ECG equipment (12-lead surface), instructions, and training (when requested). Subjects should be in supine position and resting for ≥10 minutes before study-related ECGs. At screening, results from the central ECG reader (triplicates taken at least 1 minute apart) will be averaged to determine eligibility and must meet the eligibility criteria of QTc ≤480 ms. Thereafter, single ECGs are done at each timepoint (Table 4-2). However, if a machine-read ECG registers a QTc (either Bazett's or Fridericia's) of ≥501 ms or >60 ms above baseline then a second ECG must be done after 5 minutes. If at any point, a subject experiences a Grade ≥3 QTc prolongation according to the machine on site (i.e., the subject has 2 consecutive ECGs taken ≥5 minutes apart with a QTc that is ≥501 ms, demonstrate a >60-ms change from baseline, or show other ventricular dysrhythmias per Table 4-1), ACP-319 must be held pending acquisition of the QTc results from the centralized review. If centralized review confirms both ECG QTc readings are ≥501 ms, show a >60 ms change from baseline, or show other ventricular dysrhythmias per Table 4-1, then the subject should have the ACP-319 held until those abnormalities resolve to baseline values and receive any further ACP-319 at a reduced dose level. Conversely, if the centralized review shows that both ECG QTc readings are ≤500 ms and the change in QTc is ≤60 ms from baseline, dosing may be restarted at the same dose level, but missed doses will not be made up.

Protocol: ACE-LY-001

Table 4-2. ECG Acquisition Times

| Study Segment | Day | ECG Acquisition Times |
|-----------------|------------|------------------------------------------------------------------------------------------------------------------------------|
| Screening | | Triplicate at least 1 min apart |
| Cycle 1 | 1 | Single ECG predose, and 1, 2, 4, and 6 hours after 1 st dose; window for ECGs at 1, 2, 4, 6 hours is ±10 minutes. |
| Cycle 1 | 8 | Single ECG predose, and 1, 2, 4, and 6 hours after dose; window for ECGs at 1, 2, 4, 6 hours is ±10 minutes |
| Cycle 1 | 15, 22, 28 | Single ECG 1 hour (±10 minutes) postdose |
| Cycle 2 | 15, 28 | Single ECG anytime during the visit |
| Cycles 3 to 6 | 28 | Single ECG anytime during the visit |
| Cycles 9 and 12 | 28 | Single ECG anytime during the visit |

Abbreviations: CTCAE = Common Terminology Criteria for Adverse Events;

ECG = electrocardiogram.

All timepoints relative to the morning dose.

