Note: Under Amendment 6 of this protocol, all active subjects will receive acalabrutinib monotherapy (100 mg BID).

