3.9 MANAGEMENT OF SPECIFIC AEs

Recommendations for modifications of the dosing regimens based on the drug and the type and severity of AEs or laboratory abnormalities are provided in Table 3-2. The recommendations provided in Table 3-2 comprise only guidelines; variations from these recommendations may be warranted based on an investigator's individual judgment in considering potential risks, benefits, and therapeutic alternatives available to each subject. Whenever possible, any interventions for potential treatment-related AEs should be discussed between the investigator and the medical monitor before implementation.

Please refer to Section 4.1.9 for dose modifications based on QTc AEs.

Table 3-2. Recommendations for Acalabrutinib and ACP-319 Dose Modifications Based on Type and Severity of Treatment-Related Adverse Events or Laboratory Abnormalities

| Recommendation | | | | | |
|----------------------------------------------------------------------------------|--------------------------------------------------------------------------------------------------------------------------------------------------------------------------------------------------------------------------------------------------------------------|--------------------------------------------------------------------------------------------------------------------------------------------------------------------------------------------------|--|--|--|
| NCI CTCAE Grade | Acalabrutinib | ACP-319 | | | |
| Gastrointestinal Inflammation/Diarrhea | | | | | |
| Grade 1 Mild diarrhea: Increase of < 4 stools per day over baseline | Provide antidiarrheal (e.g., loperamide) and maintain current acalabrutinib dose level and schedule. Provide antidiarrheal (e.g., loperamide). Withhold acalabrutinib until Grade <1. | Provide antidiarrheal (e.g., loperamide) and maintain current ACP-319 dose level and schedule. Provide antidiarrheal (e.g., loperamide) and maintain current ACP-319 dose level and | | | |
| Grade 2 Moderate diarrhea: Increase of 4–6 stools per day over baseline | Resume acalabrutinib at current dose level. If rechallenge results in recurrence, may resume at initial or lower dose level at investigator discretion (if applicable). Consider addition of anti-inflammatory (e.g., sulfasalazine, budesonide). | schedule. Monitor at least weekly until resolved. Consider addition of anti-inflammatory (e.g., sulfasalazine, budesonide). | | | |

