| Grade ≤2 | Maintain current dose level and schedule. | Maintain current dose level and schedule. | | | |
| Grade 3 | Maintain current dose level and schedule. | Maintain current dose level and schedule. Monitor ANC at least 1x per week. | | | |
| Grade 4 | Maintain current dose level and schedule and monitor ANC at least 1x per week. If Grade 4 neutropenia lasts for >7 days (neutrophil growth factors are permitted per ASCO guidelines [Smith et al. 2015b] and use must be recorded on the CRF), modify dose as instructed in Table 3-1. | Withhold ACP-319. Monitor ANC at least 1x per week until ANC ≥0.5 x 10 ⁹ /L, then resume ACP-319 at lower dose level (if applicable). | | | |
| | Thrombocytopenia | 1 | | | |
| Grade ≤2 | Maintain current dose level and schedule. | Maintain current dose level and schedule. | | | |
| Grade 3 | If no significant bleeding, maintain current dose level and schedule. In the presence of significant bleeding, modify dose as instructed in Table 3-1. | Maintain current dose level and schedule. Monitor PLT at least 1x per week. | | | |
| Grade 4 | Modify dose as instructed in Table 3-1. | Withhold ACP-319. Monitor PLT at least 1x per week until PLT ≥25 x 10 ⁹ /L, then resume ACP-319 at lower dose level (if applicable). | | | |
| | Rash | T | | | |
| Grade 1 | Maintain current dose level and schedule. | Maintain current dose level and schedule. | | | |
| Grade 2 | Maintain current dose level and schedule. | Withhold ACP-319 until Grade ≤1, consider systemic corticosteroids. May resume ACP-319 at initial or lower dose (if applicable) at investigator discretion. | | | |

Protocol: ACE-LY-001

Table 3-2. Recommendations for Acalabrutinib and ACP-319 Dose Modifications Based on Type and Severity of Treatment-Related Adverse Events or Laboratory Abnormalities

| | Recommendation | | |
|-------------------------------------|-----------------------------------|---------------------------------|--|
| NCI CTCAE Grade | Acalabrutinib | ACP-319 | |
| | Withhold acalabrutinib until | Discontinue ACP-319 | |
| | Grade ≤1, consider systemic | permanently. | |
| Grade = 3 or 4 | corticosteroids. May resume | | |
| 014de - 3 01 4 | acalabrutinib at initial or lower | | |
| | dose level (if applicable) at | | |
| | investigator discretion. | | |
| QTC Interval Prolongation | | | |
| | | Refer to Section 4.1.9. | |
| Other Nonhematologic Adverse Events | | | |
| Grade ≤2 | Maintain current dose level | Maintain current dose level and | |

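### Table 4-1 puts an isolated QTc of 501 ms or more in both Grade 3 and Grade 4, so the acalabrutinib action is contradictory; and Section 3.0 drops nonserious ventricular arrhythmias that Section 6.2.4 requires

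*Protocol*

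**What the plan says.** **Treatment.** Section 3.0 states "Under Amendment 6 of this protocol, all active subjects will receive acalabrutinib monotherapy (100 mg BID". ACP-319 has been stopped in every ongoing subject.

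**QTc handling.** Section 3.9 tells sites "Please refer to Section 4.1.9 for dose modifications based on QTc AEs", and the QTc row of Table 3-2 says "Refer to Section 4.1.9". In Section 4.1.9 the hold before central review is "ACP-319 must be held pending acquisition of the QTc results from the centralized review". After confirmation the subject again has ACP-319 held and is to "receive any further ACP-319 at a reduced dose level". Acalabrutinib is named in none of these steps.

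**Grading.** Table 4-1 defines Grade 3 as "QTc ≥501 ms on at least 2 separate ECGs". Grade 4 begins "QTc ≥501 ms or >60 ms change from baseline or Torsades de pointes" and continues, again joined by 'or', with polymorphic ventricular tachycardia and serious arrhythmia.

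**General dose rules.** Section 3.8 holds either drug, or both, as needed. Section 3.8.1 holds for an unmanageable, possibly related toxicity of Grade 3 or higher. Section 3.8.2 applies Table 3-1 (hold acalabrutinib, with restart at 100 mg BID allowed on the first two occurrences) to every Grade 4 toxicity, and to Grade 3 only when unmanageable.

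**Reporting.** Section 6.2.4 makes ventricular arrhythmias an adverse event of special interest for acalabrutinib, to be reported promptly whatever their seriousness or cause, and refers to Section 6.3.5. Section 3.0 lets subjects stay in this study on acalabrutinib after database closure, with data collection then limited to SAEs under Section 6.3.

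**The concern.** A site with a centrally confirmed QTc ≥501 ms in a subject on monotherapy is sent to Section 4.1.9, where every instruction concerns a drug the subject does not take. It must fall back on general rules that turn on the grade, and the grade is not unique. Two sites with the same tracings could both comply, one interrupting acalabrutinib and the other continuing it. The ambiguity also reaches the safety tables, because Section 5.4.1 summarises adverse events by CTCAE severity.

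The second issue is a conflict between two live rules. A subject who stays on acalabrutinib in this study after closure and has a nonserious ventricular arrhythmia has a reportable event under Section 6.2.4 and one outside data collection under Section 3.0.

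**Working it through.** No sample size, power or error rate is involved. The check sets the provisions side by side.

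**Step 1: grade and resulting action, as printed.**

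| Finding | Grade in Table 4-1 | Acalabrutinib action through 3.8.2 |
|---|---|---|
| One ECG with QTc ≥501 ms, no arrhythmia | 4 | Hold |
| Two ECGs with QTc ≥501 ms, no arrhythmia | 3 and 4 | Hold if read as Grade 4; hold only if unmanageable if read as Grade 3 |
| Change above 60 ms, QTc below 501 ms | 4 through the change criterion | Hold |
| Torsades, polymorphic ventricular tachycardia, serious arrhythmia | 4 | Hold |

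**Step 2: why this is a contradiction.** Any subject with two readings ≥501 ms has at least one such reading, so everyone who meets Grade 3 also meets Grade 4. Read literally, the Grade 3 row never decides a case. A single reading also ranks above the two readings required for Grade 3. A reader who gives the Grade 3 row any meaning must depart from the 'or' in the Grade 4 row, and the hold rule then changes.

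**Step 3: does the QTc-specific text settle it?** No. The provisional hold, the confirmed hold and the dose reduction in Section 4.1.9 all name ACP-319. The QTc row of Table 3-2 only points back there; I do not rely on which drug column that pointer occupies.

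**Step 4: reach.** Table 4-2 schedules no ECG after Cycle 12, and Appendix 5, the one schedule retained, covers cycles beyond 12 and has no ECG row. Triggers now come mainly from unscheduled ECGs. Section 3.11.1 advises an ECG for symptoms such as palpitations or syncope, Section 4.1.12 anticipates unscheduled ECGs, and the QTc rule in 4.1.9 is not tied to a visit.

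**Step 5: reporting after closure.**

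| Event in a subject still on acalabrutinib in this study | Section 6.2.4 | Section 3.0 after closure |
|---|---|---|
| Serious ventricular arrhythmia | Report | Report, as an SAE |
| Nonserious ventricular arrhythmia | Report | Not collected |

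The cross-reference in Section 3.0 is to Section 6.3. Section 6.2.4 lies outside it, so the reference does not bring the special-interest duty back in.

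**The case against.** **The ACP-319 target had a reason.** Section 1.13.2 reports a trend to QTcF prolongation at 400 mg of ACP-319, while Section 1.4.2 reports no QTc change with 100 or 400 mg of acalabrutinib in healthy subjects and calls the QT risk low. This stands. A reader might infer that the protocol overlooks a QT hazard of acalabrutinib; the documents do not support that. Naming acalabrutinib in Section 4.1.9 is partly a clinical choice. It does not excuse the grade overlap, because the general rules apply to acalabrutinib and depend on the grade.

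**Acalabrutinib is already covered.** A reader might infer that no rule can stop acalabrutinib for QTc prolongation. That goes too far. Sections 3.8 to 3.8.2 reach it, and a change above 60 ms, Torsades and serious arrhythmia are Grade 4 as printed, so the Table 3-1 hold applies. Even an isolated QTc ≥501 ms meets Grade 4 read literally, but only by emptying the Grade 3 row.

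**Another row of Table 3-2.** A reader might add a further competing action from the row for other nonhematologic events. QTc has its own row, and Section 3.9 says "The recommendations provided in Table 3-2 comprise only guidelines", so that row does not plainly apply. The split is between two actions: hold, or hold only if unmanageable.

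**Reporting during the study.** A reader might infer that Section 6.3.5, written for SAEs, leaves special-interest events without a route or deadline. Section 6.2.4 points to 6.3.5 for instructions, and that section gives the electronic route and its 24-hour limit. No defect is shown there.

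**Section 3.0 as the specific rule after closure.** It may have been meant to override the general collection of adverse events. It does not say that it overrides Section 6.2.4, whose duty expressly does not depend on seriousness, and Amendment 6 lists changes to both sections.

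**Conclusion.** The point holds at minor to moderate weight, in two parts. First, Table 4-1 contradicts itself for an isolated QTc ≥501 ms, so whether acalabrutinib must be held is contradictory, and the QTc-specific text in Section 4.1.9 cannot resolve it because it governs a drug no longer given. Second, Sections 3.0 and 6.2.4 conflict for nonserious ventricular arrhythmias after database closure.

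The documents give no count of affected subjects and the reach is probably small. No efficacy endpoint or estimate is affected; what is affected is treatment handling, the severity grade of QTc events, and a narrow class of late safety reports. The conclusion rests on reading the 'or' in the Grade 4 row as printed. Which grade was intended should be confirmed against the CTCAE version in use, which is not at hand here.

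**What to change.** **1. Table 4-1.** Make Grade 4 require arrhythmia: QTc ≥501 ms or a change above 60 ms, together with Torsades, polymorphic ventricular tachycardia, or signs or symptoms of serious arrhythmia. Leave isolated QTc ≥501 ms on two ECGs as Grade 3 only.

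**2. Section 4.1.9.** Add that, for subjects on acalabrutinib monotherapy, a centrally confirmed QTc ≥501 ms or change above 60 ms is handled per Table 3-1. This sentence is needed alongside the first change, because an isolated change above 60 ms would no longer reach Table 3-1 as a Grade 4 event. Add also that Torsades, polymorphic ventricular tachycardia or symptomatic serious arrhythmia triggers the Table 3-1 hold at once. Making every action wait for central confirmation would delay a hold that already applies to these events.

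**3. Section 3.0.** Extend the post-closure exception to SAEs and adverse events of special interest, citing Sections 6.2.4 and 6.3.

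Naming adverse events of special interest in Section 6.3.5 is an optional clarification.

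**Cost.** No added visits, ECGs or tests. Acalabrutinib will occasionally be interrupted, and Section 3.8.1 warns that as little as 7 days off drug can transiently worsen disease; awaiting central confirmation for isolated QTc findings limits this. A few more nonserious reports will be filed after closure.
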